APPENDIX F INSTRUCTIONS FOR OCULAR SURFACE STAINING

CORNEAL STAINING

The Investigator or designee assesses the corneal staining after instillation of fluorescein dye in the eye using the following method.

1. Place one drop of commercially available saline on a standard fluorescein strip. Take care to avoid applying the saline to the fluorescein strip holder. Do not shake the strip. Wait ten seconds after application of the saline before proceeding.
2. Instruct the patient to look down and towards the opposite hand from the eye receiving the stain. It may be helpful to ask the subject to fixate on his/her own thumb. Place the subject's thumb to rest on the opposite leg to achieve inferior fixation of approximately 45 degrees down and 20 degrees nasal.
3. Retract the upper eyelid. Introduce the fluorescein strip at an approximate 30-degree angle and touch the superior temporal bulbar conjunctiva, preferably 4 mm or more from the limbus, for 2 seconds, so that 1-2 mm of the flat side makes contact with the ocular surface. Withdraw the strip and release the upper lid.

NOTE: *If the size of the strip prevents application to the desired position on the superior temporal bulbar conjunctiva, apply the strip to a location on the bulbar conjunctiva as close as possible to the preferred position.*

4. Instruct the subject to close the eyelids completely three times. Wait 1.5 minutes (90 seconds) before evaluating the ocular surface for staining.
5. To observe the fluorescein staining, evaluate the subject's eye under the slit-lamp biomicroscope using a cobalt blue filter transmitting 330 to 400 nm and a beam approximately 4 mm wide and 10 mm high.
6. Examine the entire cornea. Grade the corneal staining observed in the central, inferior, nasal, temporal and superior regions as shown in Figure 4 on a scale of 0 to 3 based on the Report of the National Eye Institute/Industry Workshop on Clinical Trials in Dry Eye. Document the staining grade.

[figure not shown]

Figure 4: Diagram of Corneal Regions for Fluorescein Staining Grading

CONJUNCTIVAL STAINING

The Investigator or designee assesses the conjunctival staining after instillation of lissamine green dye in the eye using the following method.

1. Place one drop of commercially available saline on a standard lissamine green strip. Take care to avoid applying the saline to the strip holder. Do not shake the strip. Wait ten seconds after application of the saline before proceeding.
2. Instruct the patient to look down and towards the opposite hand from the eye receiving the stain. It may be helpful to ask the subject to fixate on his/her own thumb. Place the subject's thumb to rest on the opposite leg to achieve inferior fixation of approximately 45 degrees down and 20 degrees nasal.
3. Retract the upper eyelid. Introduce the strip at an approximate 30-degree angle and touch the superior temporal bulbar conjunctiva, preferably 4 mm or more from the limbus, for 2 seconds, so that 1-2 mm of the flat side makes contact with the ocular surface. Withdraw the strip and release the upper lid.

NOTE: *If the size of the strip prevents application to the desired position on the superior temporal bulbar conjunctiva, apply the strip to a location on the bulbar conjunctiva as close as possible to the preferred position.*

4. Instruct the subject to close the eyelids completely three times. Wait 1.5 minutes (90 seconds) before evaluating the ocular surface for staining.
5. To observe the lissamine green staining, evaluate the subject's eye under the slit-lamp biomicroscope with a beam approximately 4 mm wide and 10 mm high.
6. Examine the entire bulbar conjunctiva. Grade the conjunctival staining observed in the six regions as shown in Figure 5 on a scale of 0 to 3 based on the Report of the National Eye Institute/Industry Workshop on Clinical Trials in Dry Eye. Document the staining grade.

[figure not shown]

Figure 5: Diagram of Conjunctival Regions for Lissamine Green Staining Grading

APPENDIX G. ADVERSE EVENT AND COMPLAINT REPORTING INSTRUCTIONS

All adverse events and complaints related to using JJSV products must be reported to JJSV.

All adverse events and complaints:

For events that are not considered serious or related to the study device:

1. Record the event and/or complaint on the case report form that corresponds to the visit during which awareness of the event occurred. Additionally, a complaint may be reported via a telephone call to JJSV.
2. Complete the case report form (CRF) in a timely manner.

Serious Adverse Events or device deficiencies that may have led to a serious event

In the event of a serious event (i.e., life- or sight-threatening incident) whether or not related to the device, or a device deficiency that may have led to a serious event, the investigator shall:

1. Notify JJSV immediately (no more than 24 hours after learning of the event) as follows:
 - a. Contact the following JJSV personnel by phone and/or email:
 - b. Complete an Adverse Event Form and submit to JJSV

Non-serious, device-related Events:

For events that are not considered serious but are believed related to the study device (ADEs):

1. Complete an Adverse Event Form
2. Ensure the data are submitted to JJSV within a timely manner.

1 INTRODUCTION

This document summarizes the statistical methods to be implemented during the analysis of data for the evaluation of the clinical use of the LipiFlow system with Activator LFD-2100. This is a prospective, open-label clinical study. The study will be conducted at up to 4 sites with minimum 50 eyes and up to 100 eyes to be treated. Each subject will undergo 1-2 visits which include informed consent, screening for study participation, and receiving the LipiFlow treatment.

The primary endpoint is successful completion of LipiFlow treatment with Activator LFD-2100 in at least 95% cases. Additional endpoints include rating of each step in the LipiFlow treatment procedure with Activator LFD-2100, rate of complications and adverse events.

Table listings are included in Appendix I.

2 ANALYSIS POPULATIONS

2.1 ANALYSIS POPULATIONS

All subjects treated who have available data will be included in the analysis population. All the questionnaire responses and the treatment reports generated by LipiFlow system after completion of treatment will be collected and analyzed to confirm successful completion of the procedure. Questionnaire responses for each item and data from the treatment reports will be summarized for Activator LFD-2100. No imputations for missing values will be used.

2.2 DATA CONVENTIONS

Descriptive statistics will typically include sample size (N), mean, standard deviation (SD), median, minimum (Min.), and maximum (Max.) as appropriate for continuous variables. For categorical data, the frequency and proportion will be computed.

3 ACCOUNTABILITY/DEMOGRAPHICS

3.1 ACCOUNTABILITY

The number of enrolled subjects will be tabulated by site. Subjects signed the informed consent but failed the screening procedures will be listed.

3.2 DEMOGRAPHICS

Subject demographic data including age, sex, race and ethnicity will be presented. Age will be summarized with descriptive statistics with mean, standard deviation, median,

minimum and maximum. The frequency distributions of sex, race and ethnicity will be tabulated.

4 STUDY ENDPOINTS

4.1 PRIMARY ENDPOINTS

SUCCESSFUL COMPLETION OF LIPIFLOW TREATMENT WITH ACTIVATOR LFD-2100 IN 95% OR MORE CASES

The treatment reports automatically generated by LipiFlow Console after completion of each treatment will show if the treatment completion is successful. The response of 'Yes' to the question of 'Were the Activators LFD-2100 able to complete a successful treatment' indicates the successful completion. The expected proportion of successful completion of LipiFlow treatment will be greater than or equal to 95%. List of eyes with unsuccessful completion of LipiFlow treatment and the corresponding comment will be provided.

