- Availability, willingness, ability and sufficient cognitive awareness to comply with study protocol, examination procedures and visit.
- Be willing to provide informed consent and authorization to disclose protected health information or equivalent documentation necessary to comply with applicable privacy laws pertaining to medical procedures.
- Ability to understand and respond in English.

Exclusion Criteria (all criteria apply to each study eye):

Subject will not be able to be in the study, if the subject:

- Has a history of certain medical conditions that have been identified as contraindications and precautions of the LipiFlow System (refer to the *LipiFlow Thermal Pulsation System Instructions for Use* for details)
- Has a history of prior eye surgery or trauma, active eye disease, or other eye abnormality in the study eye(s), which in the opinion of the investigator would confound the study results.
- Is pregnant, or is breast feeding.
- Concurrent participation or expected participation in an interventional (i.e., surgical or pharmaceutical interventional) clinical trial within 14 days prior to study screening.

STUDY ENDPOINTS:*Primary Endpoint:*

- Successful completion of LipiFlow treatment with Activator LFD-2100 in 95% or more cases.

Other Endpoints:

- Questionnaire rating of each step in the LipiFlow treatment procedure with Activator LFD-2100.
- Rate of adverse events and complications.

STUDY VISITS AND PROCEDURES:

Inclusion and exclusion qualifications will be assessed at the enrollment visit according to the inclusion/exclusion criteria.

The Informed Consent Document and Authorization for Use/Disclosure of Health Information form to comply with US Health Information Portability and Accountability Act (HIPAA) must be signed by any subjects who agree to participate in the study prior to undergoing any study-specific procedures.

After determination that all inclusion/exclusion criteria have been met, enrolled subjects will receive the LipiFlow system treatment on both eyes. The investigator or designee will complete a questionnaire regarding the clinical use of Activators LFD-2100 for each subject (see **Appendix A**).

VISIT PROCEDURES:

- 1) Informed consent.
- 2) Screening and enrollment.
- 3) Perform a pre-treatment slit lamp evaluation, non-dilated fundus exam, ocular surface staining for all the subjects, and optional meibomian gland assessment at the investigator's discretion.

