- 4) Complete a bilateral LipiFlow treatment with Activators LFD-2100 on both eyes of a subject, and collect the treatment reports automatically generated by LipiFlow console after completion of each treatment
- 5) Perform a post-treatment slit lamp evaluation and ocular surface staining.
- 6) Questionnaire: The Investigator or designee will complete a questionnaire regarding the clinical use of Activator LFD-2100 (see **Appendix A**).

DATA ANALYSIS:

The investigator or designee will complete a questionnaire on each step of the LipiFlow procedure with Activators LFD-2100 (see **Appendix A**) for each subject. The treatment reports automatically generated by LipiFlow console after the completion of each treatment will be analyzed and used to evaluate successful completion of the procedure.

SAMPLE SIZE CALCULATION:

The confidence interval approach is used to estimate precision around the true proportion of successful completion of LipiFlow treatment with Activator LFD-2100. Assuming the proportion of successful completion of LipiFlow treatment is 95%, with n= 50 eyes, a two-sided 95% confidence interval will be (89%, 100%), i.e., a precision of 6.0%.

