10. EXPERIMENTAL PLAN

10.1 OVERVIEW

The study will be conducted in accordance with the principles of the Declaration of Helsinki and in accordance with U.S. Code of Federal Regulations, ISO 14155 and all other applicable laws and regulations. The study will not begin until IRB approvals have been obtained.

Study activities may be delegated to qualified study staff, but the Principle Investigator is responsible for all study activities. Delegation must be documented before study activities commence. Individuals involved in the conduct of this study will have documented training applicable to their respective roles.

All tests in this protocol are to be performed by the investigators or designees who are representative of the end-user community for the LipiFlow system (e.g., ophthalmologists, optometrists and technicians). All tests will be performed in a clinic, an office or laboratory setting and may be observed by JJSV personnel. Three to five investigators or designees will perform the LipiFlow treatments per this protocol on approximately 25 – 50 subjects per investigator or designee, resulting in treatments in minimum 50 eyes and up to 100 eyes in total.

Informed consent will be obtained for each subject prior to any study-specific activities. The subjects may refuse participation or exit the study at any time. If new information

becomes available that may impact a subject's willingness or ability to continue participation in the study, the informed consent form will be revised, and each subject will be re-consented.

After screening and enrolment, if a subject meets all inclusion / exclusion criteria, the investigator or designee will perform a complete LipiFlow treatment with Activator LFD-2100 on both eyes of a subject.

The investigator or designee will complete a questionnaire regarding the clinical use of the Activator LFD-2100 (see **Appendix A**). The treatment reports automatically generated by LipiFlow Console after completion of each treatment will be printed out and collected. The reports will present confirmation of treatment completion together with treatment information such as the changes in pressure and temperature during the treatment.

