10.2 VISIT SCHEDULE

Each subject will have a 1-2 study visits which include informed consent, screening for study participation and performing the LipiFlow treatment with Activator LFD-2100 (see **Appendix C**). Unscheduled visits may be conducted as necessary at the discretion of the investigator for clinically-indicated follow-up.

Inclusion and exclusion qualifications will be assessed prior to study treatment. The Informed Consent Document must be signed by any subjects who agree to participate in the study prior to undergoing any study-specific procedures.

Study parameters and methods are listed as below:

- 1) Informed consent

- 2) Screening and Enrollment: including but not limited to reviewing medical and ocular history, discussing study eligibility etc.
- 3) Perform a pre-treatment slit lamp evaluation, non-dilated fundus exam, ocular surface staining for all the subjects, and optional meibomian gland assessment at the investigator's discretion.
- 4) Complete a bilateral LipiFlow treatment with Activator LFD-2100 on both eyes of a subject, and collect the treatment reports automatically generated by the LipiFlow console after completion of each treatment.
- 5) Perform a post-treatment slit lamp evaluation and ocular surface staining.
- 6) Questionnaire: The Investigator or designee will complete a questionnaire regarding the clinical use of the Activator LFD-2100 (**Appendix A**).

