10.4 ACTIVATOR SUPPLY

For all the study subjects, the Activators will be obtained from the site study consignment supplied by JJSV prior to the first study treatment. One Activator will be used on each eye of a subject. Unused back-up Activators are to be returned to the site consignment. At the completion of all study treatments, any remaining Activators will be shipped back to JJSV following the final accountability by a JJSV Study Monitor. At all times, the storage, access and use of all the consignment Activators must be controlled.

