20.2 STUDY ENDPOINTS

Primary Endpoint:

- Successful completion of LipiFlow treatment with Activator LFD-2100 in 95% or more cases.

The treatment reports automatically generated by LipiFlow Console after completion of each treatment will show if the treatment completion is successful. The frequency and proportion of successful completion of treatment will be reported. The expected proportion of successful completion of LipiFlow treatment question will be greater than or equal to 95%.

Other Endpoints:

- Questionnaire rating of each step in the LipiFlow treatment procedure with Activator LFD-2100.

For questions with a 'Yes' or 'No' response, the frequency and proportion of each question with response 'Yes' will be reported. For questions with five levels of

rating score responses, the frequency and proportion of each level of rating score responses will be tabulated. The mean and median of rating score of each question will also be reported.

- Rate of adverse events and complications.

The type and rates of adverse events will be summarized.

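### SAP 4.1 gives two unranked sources for primary success, and the questionnaire item it uses is printed as one answer for both Activators although results are counted by eye

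*SAP*

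**What the plan says.** **Source of success.** Protocol 20.2 rests the primary endpoint on the console: "The treatment reports automatically generated by LipiFlow Console after completion of each treatment will show if the treatment completion is successful". The synopsis agrees that the reports "will be analyzed and used to evaluate successful completion of the procedure", and Protocol 10.1 adds: "The reports will present confirmation of treatment completion". Protocol 20.1 and SAP 2.1 are broader. Both name the questionnaire responses alongside the reports as evidence that the procedure was completed. SAP 4.1 repeats the Protocol 20.2 sentence and follows it with a scoring rule: "The response of 'Yes' to the question of 'Were the Activators LFD-2100 able to complete a successful treatment' indicates the successful completion". No section ranks the two sources or says what happens if they disagree.

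**Unit of the questionnaire.** The synopsis says: "The investigator or designee will complete a questionnaire regarding the clinical use of Activators LFD-2100 for each subject". The Appendix A form carries a subject identifier, has no eye field and allows one response per question. Item 2 asks about Activators in the plural, and Protocol 10.4 states: "One Activator will be used on each eye of a subject".

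**Unit of reporting.** SAP 4.1 promises: "List of eyes with unsuccessful completion of LipiFlow treatment and the corresponding comment will be provided". SAP 4.2.1 also lists low questionnaire ratings by eye. SAP Appendix I gives eyes as the unit for both the primary endpoint and the questionnaire.

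**The concern.** A primary endpoint needs one deciding source and one unit. SAP 4.1 leaves three readings of item 2 open: a second criterion, a substitute for the report, or the field in which the report's result is recorded. Use of item 2 for scoring is a realistic possibility. SAP 4.1 expresses the rule through that answer, and the comments promised for unsuccessful eyes have their printed prompt under that item.

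If item 2 does decide, one printed answer has to stand for two eyes. When one eye completes and the other does not, neither 'Yes' nor 'No' is correct for both, and no rule says how to split the answer. What is at stake is the reported proportion and whether the 95% criterion, which is also the clinical hypothesis, appears to be met. Separately, a form captured once per subject but tabulated in eyes could show up to twice the true number of questionnaire responses.

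**Working it through.** **1. The plan's own figure.** Protocol 20.3 and SAP 5 assume 95% success in 50 eyes. The Wald half-width is 1.96 × √(0.95 × 0.05 / 50) = 0.0604, giving 88.96% to 101.04%. Cut off at 100%, this is the stated interval of 89% to 100% with 6.0% precision. The figure reproduces, with the eye as its unit. The source and unit question does not alter it.

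**2. Three ways to score the same data.** Assume that all n subjects are treated in both eyes, so 50 to 100 eyes means 25 to 50 subjects. Let u subjects have one failed eye and b have two.
- By eye: (2n − u − 2b) / 2n
- Reading A, 'No' if either eye failed, applied to both eyes: (2n − 2u − 2b) / 2n
- Reading B, 'Yes' if at least one eye completed, applied to both eyes: (2n − 2b) / 2n

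Reading A lies below the by-eye rate by u/2n, and Reading B lies above it by the same amount. If u = 0, so that every failure is bilateral, all three agree.

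**3. Numbers, with b = 0.**

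| Subjects | u | By eye | Reading A | Reading B |
|---|---|---|---|---|
| 25 | 1 | 49/50 = 98% | 48/50 = 96% | 50/50 = 100% |
| 25 | 2 | 48/50 = 96% | 46/50 = 92% | 50/50 = 100% |
| 25 | 3 | 47/50 = 94% | 44/50 = 88% | 50/50 = 100% |
| 50 | 3 | 97/100 = 97% | 94/100 = 94% | 100/100 = 100% |
| 50 | 5 | 95/100 = 95% | 90/100 = 90% | 100/100 = 100% |
| 50 | 6 | 94/100 = 94% | 88/100 = 88% | 100/100 = 100% |

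With 25 subjects, two one-eye failures are enough for Reading A to miss 95% when the by-eye rate meets it. Three are enough for Reading B to meet 95% when the by-eye rate misses it. With 50 subjects the corresponding counts are three and six.

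**4. How many such subjects to expect.** With success rate p per eye and between-eye correlation ρ, the chance that exactly one eye fails is 2p(1 − p)(1 − ρ). At the plan's p = 0.95 this is 0.095 × (1 − ρ). For 25 subjects the expected number is 25 × 0.095 = 2.4 at ρ = 0, 1.2 at ρ = 0.5, 0.24 at ρ = 0.9 and 0 at ρ = 1. The documents give no value for ρ, so these are illustrations over an assumed range.

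**5. Questionnaire count.** One form per subject gives 25 to 50 responses per item. The same forms counted in eyes give 50 to 100.

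**The case against.** **The Protocol already involves the questionnaire.** A reader might infer that the SAP brings in a source foreign to the Protocol. The documents do not support that: Protocol 20.1 already lists questionnaire responses with the reports. What remains is that neither document ranks them, and that only SAP 4.1 turns an answer on the form into a scoring rule.

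**The form actually used is not shown.** Appendix A asks for completion after each study case, which could mean each eye, and the electronic case report form is not in the documents. The SAP's steady use of eyes may reflect entry by eye. The explanation requested after a 'No' may also identify the failed eye. This stands: misclassification and inflated counts are conditional. The console report's unit is not stated either. It is issued per treatment, and Protocol 10.2 has the site "Complete a bilateral LipiFlow treatment with Activator LFD-2100 on both eyes of a subject", so the report cannot simply be assumed to be per eye.

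**The effect may be small.** It needs one-eye failures, a single captured answer, and that answer copied to both eyes. Reading B also needs a rater to circle 'Yes' when one of two Activators failed. If failures mostly affect both eyes, little changes. This stands too.

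**Aborted eyes.** A reader might infer that eyes whose treatment was stopped have no report and leave the denominator, turning 47/50 = 94% into 47/47 = 100%. The documents do not show this. The reports are to show whether completion was successful, unsuccessful eyes are to be listed, and the data-availability limit in SAP 2.1 applies to subjects. A subject with an aborted eye would still have a questionnaire, in which a 'No' to item 2 asks for an explanation. A rule for such eyes is a sensible safeguard, not the correction of a demonstrated error.

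**Conclusion.** The point holds in two parts of different strength. The missing ranking is plain from the text: SAP 4.1 offers the console report and item 2, and nothing says which governs. The unit mismatch is plain on the printed form, but its consequences depend on item 2 being captured once per subject and used for scoring. In that case each subject with one failed eye moves the rate by one eye, which is 2 percentage points at 50 eyes and 1 point at 100. The shift is downward or upward depending on how the rater answers. Two or three such subjects at the minimum sample size can put the result on the other side of 95%. The shift assumes bilateral treatment, shrinks as failures in the two eyes become more correlated, and is zero when all failures are bilateral.

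The endpoint is a reported count and percentage without a hypothesis test, so no error rate is affected. The matter should be fixed before analysis because it bears on the study's headline figure and the remedy is mainly wording.

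**What to change.** In SAP 4.1, replace the questionnaire sentence with a rule to this effect:

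> Success is scored for each treated eye from the console treatment report, or from the CRF field that transcribes it by eye. Every treated eye is in the denominator, and an eye in which treatment was begun but not finished counts as not successful. Where an eye has no report, completion is taken from the CRF or source record, including item 2 and its comment. Item 2 is otherwise supportive, and any disagreement with the report is listed.

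Clarify Protocol 20.1 and SAP 2.1 to match. State that the report, or the CRF field taken from it, identifies completion for each eye. In SAP 4.2.1 and Appendix I, summarise questionnaire items by subject unless the CRF records them separately for each eye; if it does, keep eyes and say so.

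The cost is a few sentences and one table label that depends on the CRF. If the items are captured by subject, the questionnaire N falls to about 25–50 from the 50–100 implied by the present label.

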3. CLINICAL HYPOTHESIS

The Activator Model LFD-2100 will provide successful LipiFlow treatments in 95% or more cases.

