4. STUDY DESIGN

Minimum 50 eyes and up to 100 eyes will be treated in this prospective, open-label clinical study. The investigator or designee will perform LipiFlow treatment with the Activators LFD-2100 on both eyes of a subject. The data from the treatment reports generated by the LipiFlow console and from the questionnaire will be used to assess the clinical utilization of the Activator LFD-2100.

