6. STUDY OBJECTIVES AND ENDPOINTS

The purpose of this study is to confirm the clinical use of the LipiFlow system with Activator LFD-2100 to successfully complete a LipiFlow treatment procedure in human subjects. Additionally, the investigator rating of the ease of use of the LipiFlow system with Activator LFD-2100 will be obtained.

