20.3 SAMPLE SIZE CALCULATIONS

The confidence interval approach is used to estimate precision around the true proportion of successful completion of LipiFlow treatment with Activator LFD-2100. Assuming the proportion of successful completion of LipiFlow treatment is 95%, with n= 50 eyes, a two-sided 95% confidence interval will be (89%, 100%), i.e., a precision of 6.0%.

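### The study is sized on the width of a 95% confidence interval, but no interval is planned for the observed primary rate that will be set against 95%

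*SAP*

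**What the plan says.** **Sizing.** Protocol 20.3 describes its basis as follows: "The confidence interval approach is used to estimate precision around the true proportion of successful completion of LipiFlow treatment with Activator LFD-2100". The synopsis gives the result: "with n= 50 eyes, a two-sided 95% confidence interval will be (89%, 100%), i.e., a precision of 6.0" per cent. SAP 5 repeats it. No power, null rate or test appears.

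**Target.** Protocol 6 states: "The purpose of this study is to confirm the clinical use of the LipiFlow system with Activator LFD-2100". Protocol 3 gives the hypothesis: "The Activator Model LFD-2100 will provide successful LipiFlow treatments in 95% or more cases". The same 95% threshold is part of the primary endpoint in Protocol 20.2 and SAP 4.1.

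**Planned primary result.** Four places bear on it:
- Protocol 20.2: "The frequency and proportion of successful completion of treatment will be reported". No unit is given.
- SAP 2.2: a general convention of frequency and proportion for categorical data, again with no unit.
- SAP 4.1: "The expected proportion of successful completion of LipiFlow treatment will be greater than or equal to 95" per cent, plus a list of unsuccessful eyes with comments. It plans neither an interval nor a test.
- SAP Appendix I: n and %, with eyes as the unit, plus the list of unsuccessful eyes.

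**Structure of the data.** Operators will "perform LipiFlow treatment with the Activators LFD-2100 on both eyes of a subject". SAP 1 describes a study "with minimum 50 eyes and up to 100 eyes to be treated". No section on the primary endpoint mentions the pairing of eyes.

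**The concern.** The plan chooses an estimation approach to fix the number of eyes and then does not carry the estimate's precision into the analysis. What remains to set against 95% is an observed proportion. The study is framed as confirming clinical use and has a numerical hypothesis, so a reader of the report will want to know how far the true rate could lie from the observed one.

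Two features make this more than a formality. The number of eyes may fall anywhere from 50 to 100, so the same observed percentage can carry quite different precision. And each subject contributes two eyes, treated by the same operator at the same session. An interval worked out from eye counts alone would be too narrow if failures tend to occur in both eyes of a subject.

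**Working it through.** **Inputs.** Assumed rate 95%, 50 eyes, two-sided 95% level (Protocol 20.3, SAP 5); 50 to 100 eyes (SAP 1); two eyes per subject (Protocol 4). The documents give no within-subject correlation, so it is assumed to lie between 0 and 1.

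**1. The plan's own interval.** Normal approximation: p ± 1.96 × √(p(1 − p)/n) = 0.95 ± 1.96 × √(0.95 × 0.05/50) = 0.95 ± 0.0604, or 89.0% to 101.0%. Cut at 100%, this is the stated (89%, 100%) with precision 6.0%. The figure reproduces. The formula passes 100% here, so it is a poor choice for reporting results.

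**2. Intervals for results that could occur.** Exact (Clopper-Pearson) limits: the lower is the 0.025 quantile of Beta(x, n − x + 1), and the upper is the 0.975 quantile of Beta(x + 1, n − x). Eyes are taken as independent.

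| Result | Observed | Exact 95% CI |
|---|---|---|
| 48/50 | 96% | 86.3% to 99.5% |
| 50/50 | 100% | 92.9% to 100% |
| 95/100 | 95% | 88.7% to 98.4% |
| 96/100 | 96% | 90.1% to 98.9% |

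For 50/50 the lower limit is 0.025^(1/50) = 0.929. Since 0.95 × 50 = 47.5, 48 is the fewest successes that reach 95% at 50 eyes. The same 96% has a lower limit of 86.3% at 50 eyes and 90.1% at 100. The choice of method matters little: Wilson limits for 48/50 are 86.5% to 98.9%.

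**3. Pairing.** With two eyes per subject and correlation r, the effective number of eyes is n/(1 + r). At 50 eyes:
- r = 0: effective n is 50, half-width 6.0%.
- r = 0.5: effective n is 33.3, half-width 7.4%.
- r = 1: effective n is 25, half-width 1.96 × √(0.0475/25) = 8.5%.

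**4. A quantity that avoids the correlation.** Take the proportion of subjects with both eyes successful. It cannot exceed the eye rate, so its lower limit is a conservative bound for the eye rate. With 25 subjects the exact lower limits are 86.3% for 25/25 (0.025^(1/25)) and 79.6% for 24/25.

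**5. Illustration only.** Suppose an observed rate of at least 95% were read as success. At 50 eyes that is P(X ≥ 48), with eyes independent:
- True rate 90%: 0.90^50 + 50 × 0.10 × 0.90^49 + 1225 × 0.10² × 0.90^48 = 0.005 + 0.029 + 0.078 = 0.112.
- True rate 92%: 0.015 + 0.067 + 0.143, which is 0.226 before rounding the terms.

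**The case against.** The best defence is that this is a small, single-arm, descriptive study of a modified part for a cleared device, judged to be of non-significant risk. It plans no test and no comparative claim. The sizing paragraph itself shows an interval reaching down to 89%, so the plan does not hide that 50 eyes give limited precision. The output includes n, % and every failed eye, so anyone can compute an eye-level interval. If the list carries subject identifiers (its columns are not specified), subjects with a failed eye could be counted as well.

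Much of this stands. The ingredients of an interval are not withheld, and the stakes are modest. But the study's own conclusion would still not rest on an interval, although an interval is the sponsor's sole reason for the number of eyes.

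Three stronger readings may tempt a reader, and the documents support none of them:
- *The plan has a pass rule with an 11% to 23% chance of accepting a device whose true rate is below target.* No pass/fail rule is written. SAP 4.1 speaks of an expected proportion, so those probabilities are conditional on a rule the documents do not contain.
- *The study fails because no result at 50 eyes puts the exact lower limit at 95%.* Nothing requires a confidence limit to reach 95%. That would be a different and much stricter criterion than the one used for sizing.
- *The sizing interval is miscalculated.* It follows from the normal approximation, cut at 100%.

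**Conclusion.** The point holds as a gap between sizing and analysis. The planned precision has no counterpart in the planned primary result, and pairing is not addressed in either. An observed 96% at 50 eyes is compatible with true rates from 86.3% to 99.5% if eyes are independent. The planning half-width of 6.0% could be as large as 8.5% if the two eyes of a subject always agree. The first range rests on independent eyes; the second rests on an assumed correlation between 0 and 1, which the documents do not give.

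This should be corrected before the analysis. It does not affect enrolment or data collection.

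**What to change.** 1. In SAP 4.1 and the primary row of Appendix I, report the by-eye proportion from the console treatment reports with a two-sided 95% CI. Name a method suited to proportions near 1: exact Clopper-Pearson, or Wilson. SAP 4.1 also lets a questionnaire answer of Yes indicate success, but Protocol Appendix A is completed once per case, with one answer covering both Activators. If that answer is the source, analyse it by subject so that it is not counted as two eyes.
2. Beside it, report an interval that allows for pairing and still works with few or no failures. One option is the exact CI for the proportion of subjects with both eyes successful, labelled as a different quantity whose lower limit is conservative for the eye rate.
3. State that the observed rate (point estimate) is what is compared with 95%, that it is reported with its CI, and that an observed rate of at least 95% does not by itself show that the true rate is at least 95%. Match the wording in Protocol 20.2.

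**Cost.** Two extra output lines and a few sentences, with no added subjects or data. The price is wider stated uncertainty and a softer claim. The subject-level lower limit is low even with no failures (86.3% for 25/25), so it must be labelled clearly to avoid being read as the eye rate.
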